2.9 Subgroup Analysis

Subgroups for secondary analysis of clinical endpoints include:

• Reference vessel diameter ≤ 2.75 mm / > 2.75 mm.

Note: Subjects with at least one target lesion \leq 2.75 mm will be classified with the small vessel subgroup.

- Subjects > 75 years of age/subjects \leq 75 years of age.
- Women/men.
- Subjects with diabetes/subjects without diabetes.
- Lesion length > 26 mm and \leq 26 mm in length.
- Single stents versus overlapping stents for lesion lengths > 26 mm.
- Stent diameter ≤ 3.0 mm or > 3.0 mm.
- Subjects with acute coronary syndrome versus non-acute coronary syndrome.

ACS will be defined as: Subjects with unstable angina or any elevated cardiac enzymes at baseline.

There is no formal hypothesis for these subgroup analyses. Subjects with an event and/or with appropriate followup will be included in this analysis. The purpose of this analysis is not to formally assess non-inferiority within each subgroup, but simply to assess consistency of results across the various subgroups.

Version 1.0	05-18-2022	Confidential	
	Do not cop	y or distribute without sponsor approval	

2.10 Poolability Analysis

The poolability of primary study results between clinical sites in the US will be analyzed and reported but there are no pre-specified tests of the statistical significance for site differences. This poolability analysis will be included in the clinical report after the primary endpoint analysis is complete.

2.11 Sex Analysis

Any differences between sexes in the primary study results between clinical sites in the US will be analyzed and reported but there are no pre-specified tests of the statistical significance for sex differences. This sex analysis will be included in the clinical report after the primary endpoint analysis is complete.

2.12 Adverse Event Analysis

Adverse events collected in the BIOFLOW-VII data will be summarized using descriptive statistics that describe the percentage of subjects experiencing an adverse event and rate of adverse event as events per subject-year. The total number of enrolled ITT subjects and cumulative duration of follow-up completed for the enrolled subjects as of the date of the report will be utilized to calculate the descriptive statistics. AE rates will be presented by System Organ Class and Sub-category for the following:

- Site-reported AEs
- Site-reported device/procedure-related AEs
- Site-reported SAEs
- Site-reported device/procedure-related SAEs

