3.2 Study Procedures and Visits

Subjects will be followed for a period of 5 years post-index procedure.

Table 3 provides an overview of the study schedule including required visits and associated follow-up windows.

Table 3: Visit Assessment Schedule / Schedule of Events

	Index Procedure	Post-Procedure Enrollment Visit	1 Month ± 7 Days	1 Year ± 30 Days	2, 3, 4, 5 Years ±60 Days	Unsched. Visit
			Telephone Interview or Office Visit	Telephone Interview or Office Visit	Telephone Interview or Office Visit	
Informed consent form ¹		X ¹				
Demographics, clinical status, medical history, pre-procedure cardiac biomarkers (CK, CKMB or troponin), CBC, cardiovascular and antiplatelet/anticoagulant medications		X ²				
Index procedure information		X ³				
Post-procedure cardiac biomarkers (CK, CKMB or troponin)		X ⁴				
Ischemic/angina status		X	X	X	X	
12-lead ECG		X	X ⁵	X ⁵	X ⁵	
Angiography to assess lesion characteristics and final stent location	X ⁶					X ⁶
AEs and SAEs ⁷		X	X	X	X	X
Antiplatelet medical therapy		X	X	X	X	X

AE = adverse event; CBC = complete blood count; CK = creatine kinase; CKMB = creatine kinase myocardial band; ECG = electrocardiogram; SAE = serious adverse event

¹ Informed consent must be obtained after the index procedure. The date of index procedure is considered day 0 and informed consent (enrollment) can occur as late as 24 hours post-index procedure.

² Retrospective collection of pre-procedure information. Laboratory results (including cardiac biomarkers and CBC) collected only if testing performed per standard of care.

³ Retrospective collection of index procedure information.

⁴ Cardiac biomarkers collected only if testing performed per standard of care. It is anticipated that cardiac biomarker testing per standard of care generally would include subjects with positive cardiac biomarkers prior to the procedure, subjects with procedural complications and subjects with signs or symptoms of possible coronary ischemia post procedure.

⁵ ECG collected only if an office visit is performed and if ECG is performed per standard of care.

⁶ Images from standard of care angiography during index procedure should be retained and may be requested for submission to Angiographic Core Lab if subject undergoes a repeat angiogram. Angiographic data collected during any repeat procedure on the target vessel(s) must be made available to the Clinical Events Committee (CEC) and Angiographic Core Lab.

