⁷ All SAEs, potential endpoint events, and AEs possibly related to the device and/or procedure will be reported for the entire study period.

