13.4 Sponsor Reporting Responsibilities

BIOTRONIK is responsible for preparing the following reports, when necessary:

Table 9: Sponsor Reporting Requirements

Type of Report	Prepared by BIOTRONIK for	Time Constraints of Notification
Withdrawal of IRB approval	FDA, all reviewing IRBs and participating investigators	Within 5 working days after receipt of notice of withdrawal of approval
Withdrawal of FDA approval	Reviewing IRBs and participating investigators	Within 5 working days after receipt of notice of withdrawal of approval
Progress report	FDA, all reviewing IRBs	Submitted every 6 months during the first 2 years of the study and annually thereafter
Final report	FDA, all reviewing IRBs and participating investigators	A final report will be submitted within 6 months after completion or termination of the study.
Study closure	FDA, all reviewing IRBs, and participating investigators	Within 30 working days of completion or decision to terminate the study.

14 Publication Policy

BIOTRONIK intends to publish the results of this clinical study. BIOTRONIK reserves the right to include the report of this clinical study in any regulatory documentation or submission or in any informational materials prepared for the medical profession. The ownership of the data shall at all times be held by BIOTRONIK.

BIOTRONIK and the study Principal Investigator reserve the right for the first publication of the clinical study results. BIOTRONIK agrees that investigators shall be permitted to present at symposia, national or regional professional meetings, and to publish in journals, theses or dissertations, or otherwise of their own choosing, methods and results of the clinical investigation after the first publication. Any prior publication in any way or form is not permitted, without approval by BIOTRONIK.

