The primary endpoint was the 12-month rate of TLF, defined as cardiac death, target vessel Q-wave or non-Q-wave MI, emergent CABG or clinically-driven TLR. The first subject was enrolled in August 2011 and enrollment was completed in March 2012.

The BIOFLOW-III registry enrolled an unselected subject population, including a high proportion of high-risk subjects presenting with diabetes (29.6%), small vessels (42.4%), acute MI (32.6%), and chronic total occlusions (4.3%). The rate of TLF was 5.1% at 12 months. The rate of ARC-defined definite or probable stent thrombosis at 12 months was 0.4%.

BIOFLOW-III did not include mandatory angiographic follow-up and the rate of 12-month TLR was 3.0%. Among subgroups, 12-month TLF rates were 7.7% in subjects with diabetes compared with 4.0% in non-diabetics, and 7.2% in subjects with acute myocardial infarction (AMI) compared with 4.0% in subjects without AMI.

At 5 years, the TLF rate was 9.3% overall with definite or probably stent thrombosis rate of 0.7%. Among subgroups, the TLF rate for diabetic subjects was 13.0% and for subjects that had presented with acute MI was 10.6%.¹⁵

BIOFLOW-IV

BIOFLOW-IV is a prospective, international, multicenter, randomized controlled trial designed to assess the safety and effectiveness of the Orsiro stent in the treatment of subjects with up to two *de novo* coronary artery lesions. A total of 579 subjects were enrolled at 46 sites in Japan and Europe. 138 subjects were enrolled in Japan and 441 subjects were enrolled at sites in Europe. The BIOFLOW-IV clinical trial consists of a randomized control trial and a pharmacokinetic sub-trial. The BIOFLOW-IV randomized controlled trial (RCT) enrolled 579 subjects with up to two *de novo* lesions \leq 26 mm in length in native coronary arteries 2.5–3.75 mm in diameter. Subjects were randomized in a 2:1 fashion to receive the Orsiro stent or the Xience Prime/Xpedition stent. The concurrent, non-randomized pharmacokinetic (PK) sub-trial at sites in Japan, enrolled 21 subjects with up to two *de novo* lesions \leq 26 mm in length in native coronary arteries 2.5–3.75 mm in diameter.

The primary endpoint for the main RCT was the 12-month TVF rate, defined as any clinically-driven TVR, target vessel Q-wave or non-Q-wave MI, emergent CABG or cardiac death. There is no primary endpoint for the PK sub-trial.

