2.8 Comparison with BIOFLOW-V

Patient demographics and target lesion characteristics will be compared with those of the BIOFLOW-V (IDE) Orsiro study cohort to ensure that the enrolled patient population is comparable with the BIOFLOW-V Orsiro (IDE) study population. The analyses at 25%, 50%, and 75% of the expected total enrollment were previously completed and the 100% enrolled population comparison will be performed. Analysis of the target lesion characteristics will be based on site-reported data for both studies since Angiographic Core Lab analysis is not systematically performed for all index procedure angiograms in BIOFLOW-VII.

Treatment difference on dichotomous variables are evaluated using Fisher's exact tests. Categorical variables were compared between studies using the Cochran-Mantel-Haenszel (CMH) Modified Ridit Scores, i.e., CMH of general association for nominal variables and CMH of row mean score for ordinal variables. Continuous variables are compared between studies using two-sample t-tests.

Additionally, comparison between summary 1-year Adverse Event rates may be performed.

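### SAP 2.12 does not split site-reported adverse events by time since the index procedure, so its pooled subject-year rate would understate any early excess of risk

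*SAP*

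**What the plan says.** SAP 2.12 defines two descriptive measures, the "percentage of subjects experiencing an adverse event and rate of adverse event as events per subject-year". Their denominators are "The total number of enrolled ITT subjects and cumulative duration of follow-up completed for the enrolled subjects as of the date of the report". It adds that "AE rates will be presented by System Organ Class and Sub-category", for four site-reported groups: AEs, SAEs, and the device- or procedure-related part of each. It sets no time window and no minimum follow-up.

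Three protocol provisions fix what goes into these figures:

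- **Start.** In the Table 3 footnotes (Protocol 3.2), "Informed consent must be obtained after the index procedure". The note in Protocol 5.2 has events from the beginning of the index procedure collected retrospectively. Peri-procedural events are therefore counted, and every ITT subject has already had the procedure.
- **End.** Also in Table 3: "All SAEs, potential endpoint events, and AEs possibly related to the device and/or procedure will be reported for the entire study period".
- **Report dates.** Progress reports to FDA (Protocol 13.4, Table 9): "Submitted every 6 months during the first 2 years of the study and annually thereafter".

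SAP 2.8 says of BIOFLOW-V: "Additionally, comparison between summary 1-year Adverse Event rates may be performed". Neither 2.8 nor 2.12 defines a 1-year AE rate.

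**The concern.** Events per subject-year is a good summary when the event rate is roughly constant over follow-up. After a stent procedure it may not be, and the procedure-related groups, two of the four, are where front-loading is most to be expected. A pooled rate then describes neither the first month nor the later years, and it declines as quiet follow-up accumulates. Someone comparing successive progress reports could take that decline for improving safety.

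The percentage has a different weakness. Its numerator grows with follow-up while its denominator is everyone enrolled, whatever their time in study, so its value depends on the report date.

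What is at stake is how the non-adjudicated AE and SAE tables are read, and whether a like-for-like figure is to hand if the BIOFLOW-V comparison in SAP 2.8 is made.

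**Working it through.** **1. The plan's own figure.** SAP 2.12 states no number. The planned final denominator of the percentage is the enrolment target, and it reproduces: 500 / 0.90 = 555.6, rounded up to 556 (SAP 2.4).

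**2. Form of the pooled rate.** Let e be events per subject in days 0-30, l the rate per subject-year afterwards, w = 30/365.25 = 0.0821 years, N the subjects past day 30 and T total subject-years. Ignoring the few losses before day 30:

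R = [N·e + l·(T − N·w)] / T = l + N·(e − l·w) / T

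R is free of T only if e = l·w, that is, if risk is constant. If e is larger, R falls towards l as T grows.

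**3. Front-loading in the prior Orsiro data (proxy only).** Protocol section 15 gives three 5-year TLF series; for BIOFLOW-III, for example, "At 5 years, the TLF rate was 9.3% overall". Crude pooled rate = 5-year % / 5; later yearly rate = (5-year % − 1-year %) / 4; ratio = 1-year % / pooled rate.

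| Study | 1 year | 5 years | Pooled per 100 subject-years | Years 2-5, per year | Ratio |
|---|---|---|---|---|---|
| BIOSCIENCE | 6.5% | 20.2% | 4.04 | 3.43 | 1.6 |
| BIOFLOW-III | 5.1% | 9.3% | 1.86 | 1.05 | 2.7 |
| BIOFLOW-II | 6.5% | 10.4% | 2.08 | 0.98 | 3.1 |

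These count first events, ignore attrition in the denominator, and come from TLF definitions that include emergent CABG. Shorter series in the same section are not directly comparable: BIOFLOW-V TLF 6.2% to 7.5% at 2 years, ratio 6.2/3.75 = 1.7; BIOFLOW-IV TVF 5.1% to 10.4% at 3 years, 5.1/3.47 = 1.5; BIO-RESORT TVF 55/1169 = 4.7% to 8.5% at 3 years, 4.7/2.83 = 1.7; BIOFLOW-I (30 subjects) 6.7% to 13.7% at 2 years, 6.7/6.85 = 1.0.

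**4. Drift of the rate with report date.** Enrolment follows the milestones in Protocol section 18 (1, 10, 100 and 556 subjects at months 3, 5, 9 and 18 after protocol approval), with 10% attrition in year 1 (SAP 2.4). Attrition of 3% per year after that, and all values of e and l, are assumptions. Subject-years are then T = 763 at month 30 (May 2022, the date of SAP version 1.0) and T = 2412 at month 81 (planned study completion). N·w = 556 × 0.0821 = 45.7.

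Example with e = 0.05 and l = 0.05 at month 30: [27.8 + 0.05 × (763 − 45.7)] / 763 = 63.7/763 = 8.3 per 100 subject-years.

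| e; l | Days 0-30 rate (e/w) | Rate after day 30 | Pooled, month 30 | Pooled, month 81 | Fall |
|---|---|---|---|---|---|
| 0.10; 0.10 | 121.8 | 10.0 | 16.7 | 12.1 | 1.4-fold |
| 0.10; 0.02 | 121.8 | 2.0 | 9.2 | 4.3 | 2.1-fold |
| 0.05; 0.05 | 60.9 | 5.0 | 8.3 | 6.1 | 1.4-fold |
| 0.03; 0.015 | 36.5 | 1.5 | 3.6 | 2.2 | 1.6-fold |
| 0.0082; 0.10 (constant risk) | 10.0 | 10.0 | 10.0 | 10.0 | none |

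All rates are per 100 subject-years. The windowed rates do not depend on report date.

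**5. The percentage.** In the 0.05; 0.05 case, subjects with any AE rise from 10.8% at month 30 to 23.1% at month 81. The share with an event in days 0-30 is 4.65% at month 18 and 4.88% (= 1 − exp(−0.05)) from month 24 onward. Even under constant risk the any-AE percentage rises, from 12.8% to 35.2%. Later follow-up adds events to it and removes none.

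**6. Comparison within the SAP.** SAP 2.6 evaluates death, MI, MACE, TLF and TVF before discharge, at 1 month, at 1 year and yearly to 5 years. A subject counts if the event occurred or follow-up is adequate (at least 23 days for 1 month, 330 days for 1 year, and so on). SAP 1.4 classifies stent thrombosis as acute, subacute, late or very late. SAP 2.12 has neither device.

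**The case against.** The strongest reply is that the early stent risks that matter most are already well covered. Death, MI, revascularisation and stent thrombosis are adjudicated and reported at fixed time points, and Kaplan-Meier analysis is planned for the primary endpoint (SAP 2.3). This stands, and it confines the point to AEs and SAEs that are not adjudicated endpoints. A reader might infer from SAP 2.12 that early stent risk goes unreported; SAP 2.6 shows otherwise.

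Second, the numerical evidence is TLF, not AEs. This also stands. SAEs include qualifying hospitalisations over 5 years and may be much less front-loaded; under constant risk the rate does not drift at all. In BIOSCIENCE the later years were not quiet, at about 3.4% per year.

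Third, a reader might infer that both figures dilute early risk and will seem to improve. That fails for the percentage, which is cumulative and rises.

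Fourth, a reader might expect a very large drift. Starting the 0.05; 0.05 case at month 6 gives 42.7 falling to 6.1. But month 6 rests on about 32 subjects and 3 subject-years, and on the planned milestones it precedes this SAP by two years. SAP 2.8 also records the 25%, 50% and 75% enrolment comparisons as already done. Actual enrolment dates are not given.

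Fifth, SAP 2.8 does contemplate a 1-year AE comparison and nothing in 2.12 forbids producing one. That is correct; what is missing is a definition and a table that yields it.

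Finally, windowed results for every class and sub-category with 556 subjects would leave many sparse cells. That is a fair limit on the remedy.

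**Conclusion.** The point holds as a low-severity, cheap improvement. SAP 2.12 provides no breakdown by time since the index procedure. If AE risk is front-loaded, its subject-year rate understates early risk and declines with report date without any change in risk. On the 5-year TLF proxy, the year-1 rate is 1.6 to 3.1 times the pooled rate. Under the assumed AE rates above, the pooled rate falls 1.4- to 2.1-fold from the SAP date to study completion, and not at all if risk is constant. By then the larger issue is the gap between the 0-30 day rate and the pooled rate (60.9 against 6.1 per 100 subject-years in the middle scenario), not the remaining drift.

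These sizes rest on TLF standing in for AEs, on assumed early and late AE rates, on assumed attrition after year 1, and on planned rather than actual enrolment dates. The structural finding needs none of them: there is no time split, no minimum follow-up and no defined 1-year AE figure. The tables are descriptive. The primary test, its sample size and the adjudicated endpoints are unaffected.

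**What to change.** Keep both cumulative summaries in SAP 2.12 and add the following for each of the four AE groups, overall and by class where counts allow:

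- Events, subject-years at risk and the rate within fixed windows from the index procedure: 0-30 days, 31 days to 1 year, and each later year.
- The percentage of subjects with at least one event by 30 days and by 1 year, using either the SAP 2.6 follow-up rule or a Kaplan-Meier or cumulative incidence estimate. Choose one method in advance.

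State the day count meant by 1 year (Protocol 3.3.2 centres that visit on day 360), and name the 0-1 year figure in SAP 2.8 as the one to use if AE rates are compared with BIOFLOW-V.

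The cost is a paragraph of SAP text and a change to the AE table program. No new data should be needed, assuming event onset dates are recorded; SAP 2.14 already sorts events by date of occurrence. The downside is longer tables with some sparse cells.

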2.13 Additional Analyses

The following data collected in BIOFLOW-VII will be summarized using descriptive statistics:

- Antiplatelet medical therapy.
- MI event rates utilizing alternative MI definitions of Third Universal⁴, the BIOFLOW-V protocol definition³, and Academic Research Consortium (ARC)⁸ definition as specified in the CEC Charter.
- TLF event rates at 1 year utilizing alternative MI definitions, including Third Universal⁴, the BIOFLOW-V protocol definition³, and Academic Research Consortium (ARC) definition⁸.

2.14 COVID-19 Data Collection and Sensitivity Analysis

Per the FDA guidance document "Guidance on Conduct of Clinical Trials of Medical Products during COVID-19 Public Health Emergency", dated March 2020 and updated on August 20, 2021⁹, the following guidance recommendations will be implemented as noted below each point.

- 1) Contingency measures implemented to manage study conduct during disruption of the study because of COVID-19 control measures.
 - BIOTRONIK will include COVID-19 contingency measures in the clinical report.
- 2) A listing of all participants affected by the COVID-19 related study disruption by unique subject number identifier and by investigational site, and a description of how the individual's participation was altered.
 - The detailed listings of Protocol Deviations and Protocol Violations included in the clinical report, broken out by subject and protocol noncompliance (PNC) occurrence, will indicate that the PNC was impacted by COVID-19, if reported as such by the site.

3) Analyses and corresponding discussions that address the impact of implemented contingency measures (e.g., trial participant discontinuation from investigational product and/or study, alternative procedures used to collect critical safety and/or efficacy data) on the safety and efficacy results reported for the study.

The subject's COVID-19 status is collected for each adverse event for the study. Events occurring prior to the EDC release adding this data collection (July 2, 2020) were retrospectively updated to collect this data.

Additionally, the CEC will adjudicate the COVID status and assessment of event relationship to COVID-19 for all potential endpoint events.

A secondary sensitivity analysis of the primary endpoint according to COVID-19 prevalence will be performed based on CEC adjudicated event data. This sensitivity analysis will be initially performed in the clinical report after the primary endpoint analysis is complete.

- 1) Sensitivity analysis will be performed to exclude death, protocol-defined MI, and ST events from endpoint analyses that occurred in subjects adjudicated to have a Positive (confirmed positive testing) COVID-19 status.
- Sensitivity analysis will be performed to exclude death, protocol-defined MI, and ST events that occurred in subjects adjudicated to have a Positive (confirmed positive testing) or Suspected, not confirmed (no testing) COVID-19 status.
